9.3.3 Removal of Subjects From Therapy or Assessment

The investigator may discontinue treating a subject with study treatment or withdraw the subject from the study at any time for safety or administrative reasons. The subject may decide to discontinue study treatment or withdraw from the study at any time for any reason. The reason for discontinuation will be documented. If a subject discontinues study treatment, the subject will enter the Posttreatment Phase and complete protocol-specified off-treatment visits, procedures, and survival follow-up unless the subject withdraws consent. The investigator should confirm whether a subject will withdraw from study treatment but agree to continue protocol-specified, off-treatment study visits, procedures, and survival follow-up, or whether the subject will withdraw consent. If a subject withdraws consent, the date will be documented in the source documents. The Subject Disposition case report form (CRF) page will be completed indicating the reason for discontinuation from treatment. In addition, the date of last dose of study drugs will be recorded on the Study Drug Dosing CRF page.

In subjects who discontinue study therapy without documented disease progression, every effort should be made to continue monitoring their disease status by radiologic imaging every 9 weeks \pm 1 week during Year 1, and every 9 to 12 weeks \pm 1 week thereafter according to standard of care, until (1) the start of new anticancer treatment, (2) disease progression (3) death, or (4) the end of the study, whichever occurs first.

All subjects will be followed for survival until death, except where a subject withdraws consent or the sponsor chooses to halt survival follow-up after completion of the primary study analysis.

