9.5.2.1 Schedule of Procedures/Assessments

Table 8 presents the schedule of procedures and assessments for the study.

Table 8 Schedule of Procedures/Assessments

Phase	Pretreatment	Treatment		Posttreatment	
Period	Screening	Treatment Cycle 1 Through Last Cycle (21-day cycle)		End of Treatment	Follow-up ^o
Day	Days -21 to -1	Day 1 (includes Baseline C1/D1)	Day 8	Within 30 ^a days of final treatment	Every 12 weeks
Assessments					
Informed consent	X				
Inclusion and Exclusion Criteria	X				
Demographic ^b	X				
Medical/surgical history	X				
TNM Staging ^c	X				
mTNBC diagnosis	X				
Prior anticancer therapy	X				
Pregnancy test ^d	X				
PK ^e		X	X		
Tumor tissue for PD-L1 expression	X				
ECG ^f	X	X ^f	X ^f		
Hematology ^g	X	X	X	X	
Chemistry ^h	X	X		X	
TSH and free T4 levels ⁱ	X	X		X	
Urinalysis (dipstick) ^j	X	X		X	
ECOG	X	X		X	
Vital signs	X	X	X	X	
Physical examination ^k	X	X	X	X	
Eribulin mesylate ^l		X	X		
Pembrolizumab ^m		X			
Disposition				X	

Table 8 Schedule of Procedures/Assessments

Phase	Pretreatment	Treatment		Posttreatment	
Period	Screening	Treatment Cycle 1 Through Last Cycle (21-day cycle)		End of Treatment	Follow-up ^o
Day	Days -21 to -1	Day 1 (includes Baseline C1/D1)	Day 8	Within 30 ^a days of final treatment	Every 12 weeks
Tumor assessments ⁿ		Throughout Study			X
Adverse events/SAEs		Throughout Study			X
Concomitant medications		Throughout Study			
Survival information ^o				X	

AE = adverse event, β -hCG = beta-human chorionic gonadotropin, C1D1 = Cycle 1 Day 1, CT = computerized tomography, eCRF = electronic case report form, ECG = electrocardiogram, ECOG = Eastern Cooperative Oncology Group, CR = complete response, irCR = immune-related Complete Response, IV = intravenous, PK = pharmacokinetic, SAE = serious adverse event, MRI = magnetic resonance imaging, RBC = red blood cells, TNM = tumor-node-metastases, TSH = thyroid stimulating hormone, T4 = thyroxine, WBC = white blood cell.

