9.5.5 Completion/Discontinuation of Subjects

Discontinuation of study treatment does not represent withdrawal from the study.

A subject must be discontinued from study treatment but continue to be monitored in the study for any of the following reasons:

- Recurrent Grade 2 pneumonitis
- Discontinuation of treatment may be considered for subjects who have attained a confirmed CR that have been treated for at least 8 cycles (24 weeks) with pembrolizumab and had at least 2 doses of pembrolizumab beyond the date when the initial CR was declared.
- Completion of 35 treatments (approximately 2 years) with pembrolizumab.

Note: The number of treatments is calculated starting with the first dose of pembrolizumab.

The investigator may withdraw the subject from the study at any time for safety or administrative reasons. A subject may elect to discontinue the study at any time for any reason. All subjects who discontinue the study are to complete the End of Treatment procedures indicated in the Schedule of Procedures/Assessments ([Table 8](#)).

The investigator will promptly explain to the subject involved that the study will be discontinued for that subject and will provide appropriate medical treatment and other

necessary measures for the subject. A subject who has stopped returning for visits will be followed up by mail, phone, or other means to gather information such as the reason for failure to return, the presence or absence of AEs, and clinical courses of signs and symptoms.

Subjects who discontinue early from the study will be discontinued for 1 of these reasons: AE(s), lost to follow-up, subject choice, (ie, subject chooses to discontinue from the treatment but is willing to participate in the Follow-Up portion of the study), progression of disease, withdrawal of consent (ie, subject no longer wishes to participate in the study and be contacted), pregnancy, sponsor discontinuation of the study, or other. Subjects will be judged as lost to follow-up only if they cannot be reached after 3 documented attempts (at least 1 week apart) by the site to contact them.

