6.1.2 Secondary Endpoints

The secondary efficacy endpoints are as follows:

- **Progression-Free Survival (PFS)** - defined as the time from date of first dose of study drug to date of first documentation of disease progression or death, whichever occurs first.
- **Overall Survival (OS)** – defined as the time from the date of first dose of study drug until date of death from any cause.
- **Duration of Response (DOR)** – defined as the time from the date that a confirmed objective response is first documented to the date of PD or death due to any cause for those subjects with a confirmed PR or CR.
- **Clinical Benefit Rate (CBR)** – defined as the proportion of subjects who had BOR of CR, PR, or durable SD (≥ 24 weeks).
- Estimates of ORR, PFS, OS and DOR in the PD-L1 Positive Set.

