6.2.2 Subject Disposition

The number (percentage) of enrolled and treated subjects will be summarized as well as subjects who discontinued single drug and subjects who discontinued the combination treatment and reasons for discontinuation. Survival status at the last follow-up visit before data cutoff date will be summarized as well. In addition, the number (percentage) of subjects who remain in each phase at data cutoff date (i.e. treatment phase) will be summarized.

Subject disposition will be summarized by stratum and combined.

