6.4.2 Secondary Efficacy Analyses

PFS, OS and DOR

Progression-Free Survival (PFS), Overall Survival (OS) and Duration of Response (DOR) will be analyzed using Kaplan-Meier product-limit estimates. Median PFS and OS and the survival rate of PFS (at 6, 9 and 12 months) and OS (at 6, 12 and 18 months), probability of DOR \geq 6, 9 and 12 months will be presented with two-sided 95% CIs, if they can be estimated from the model. Censoring rules and data handling are described for each variable in [Section 8](#) of this SAP.

The probability of PFS, OS and DOR will be plotted over time. The median, first and third quartiles from Kaplan-Meier estimation for PFS, OS and DOR will be provided with 95% CIs if estimable.

Clinical Benefit Rate

A 2-sided Clopper–Pearson 95% CI will be constructed for calculating exact binomial intervals.

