Definition of BOR by irRECIST

- Investigator Review

Subjects who experience PD defined by RECIST1.1 will have a confirmation scan at least 4 weeks apart to confirm PD (irPD). Subjects may continue receiving study treatment while waiting for confirmation of irPD if they are clinically stable. If a subject discontinued study treatment without confirmation of irPD, the subject will be counted as irPD.

Tumor assessments after any new anti-cancer therapy, including the palliative radiotherapy, will be deleted in defining BOR. The overall time point tumor response data collected via both the CRF of the irRECIST and the CRF of the RECIST 1.1 will be used. Simply add prefix 'ir' to CR/PR/SD/PD/NE from RECIST 1.1 and follow the definition of BOR per RECIST 1.1 to define BOR per irRECIST (irCR/irPR/irSD/irPD/irNE). Table 2 describes the scenarios of PD by RECIST 1.1 followed by different confirmation scans.

Table 2. BOR by irRECIST for Scenarios with PD (defined by RECIST 1.1) Followed by Subsequent Scans

Timepoint 1 Overall Response	Timepoint 2 (\geq 4 weeks since Timepoint 1) Overall Response	BOR by irRECIST
PD	CR ^a	If subject has been followed for \geq 4 weeks and CR is confirmed, BOR is irCR. If CR not confirmed, then follow same rule as BOR by definition of RECIST 1.1.
PD	PR ^a	If subject has been followed for \geq 4 weeks and PR is confirmed, BOR is irPR. If PR not confirmed, then follow same rule as BOR by definition of RECIST 1.1.
PD	SD ^b	irSD
PD	PD ^c	irPD
PD	NE	irPD
PD		irPD, if no confirmation scan.

^a The subject should be followed for \geq 4 weeks to confirm the CR/PR.

^b The subject is on the study treatment and followed for further tumor assessments.

^c PD is confirmed. The subjects should be discontinued from the study treatment, and no further tumor response assessments will be performed.

Other exploratory endpoints using irRECIST: ORR, PFS, DOR, CBR and DCR will be derived similarly as those using RECIST1.1; but the derivation will be based on irCR, irPR, irSD and irNE instead of CR, PR, SD and NE.

- Independent Imaging Review

BOR by irRECIST for IIR data will follow the same principle as above except tumor assessments by mRECIST 1.1(modified RECIST 1.1) criteria for the time points up to PD are used.

Censoring rule for OS

Subjects who are lost to follow-up or withdrawal from study will be censored at the last date the subject was known to be alive, and subjects who remained alive will be censored at the time of data cutoff.

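### The OS rule censors subjects still alive at the data cutoff without requiring confirmation that they were alive then, so OS can be slightly overstated if late deaths are unknown at analysis

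*SAP*

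**What the plan says.** The OS censoring rule in SAP section 8 is one sentence with two parts. The first: "Subjects who are lost to follow-up or withdrawal from study will be censored at the last date the subject was known to be alive". The second: "subjects who remained alive will be censored at the time of data cutoff". SAP 6.1.2 gives OS as "defined as the time from the date of first dose of study drug until date of death from any cause". SAP 6.4.2 reports a Kaplan-Meier median and rates at 6, 12 and 18 months with 95% confidence intervals, and plans no OS test.

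Four other places decide which part of the rule applies to whom:

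- Protocol Table 8 (section 9.5.2.1) heads the Follow-up column "Every 12 weeks".
- Protocol 9.5.5 sets a demanding test for loss: "Subjects will be judged as lost to follow-up only if they cannot be reached after 3 documented attempts (at least 1 week apart".
- Protocol 9.3.3 keeps survival follow-up open: "All subjects will be followed for survival until death, except where a subject withdraws consent or the sponsor chooses to halt survival follow-up". Under Amendment 05, Protocol 9.1.3 and Table 8 footnote o end post-treatment follow-up.
- SAP 6.2.2 describes the status to be tabulated: "Survival status at the last follow-up visit before data cutoff date will be summarized as well". That visit can fall before the cutoff.

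**The concern.** The SAP does not define the group that remained alive, and no passage makes confirmation on or after the cutoff a condition of belonging to it. In practice the group is everyone not known to be dead, lost or withdrawn. A subject last contacted alive some weeks before the cutoff, with the next contact not yet due, falls into it. So does a subject whose follow-up stopped under Amendment 05 rather than by loss or withdrawal. Both are censored at the cutoff, although the last evidence that they were alive is older.

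If such a subject died in the gap and the death is unknown at analysis, the Kaplan-Meier estimate counts the gap as survival. Under this rule an unknown death can only lengthen apparent survival. The trial has one arm, so no concurrent control shares the error. The SAP is stricter for its other time-to-event endpoints: PFS (Table 3, row 3) and DOR censor at the last adequate radiologic assessment.

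**Working it through.** The documents give no OS sample size, event count, expected median or cutoff date, so there is no stated OS figure to reproduce. The size has to be illustrated.

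**Inputs from the documents**

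- N = 170 (SAP section 5).
- Accrual August 2015 to October 2018, 38 months (Protocol Synopsis).
- Contact interval w = 12 weeks = 84/30.4375 = 2.76 months (Protocol Table 8).
- Two values for the true median OS, from Protocol Table 1: 8.9 months (pembrolizumab, KN086) and 439 days = 14.4 months (eribulin, Study 301).

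**Assumptions not in the documents**

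- Uniform accrual and exponential survival.
- Cutoff 3 or 9 months after the end of accrual.
- Every subject contacted only every 12 weeks.
- A share q of the deaths between last contact and cutoff is known at analysis. q = 0 is the worst case; q = 1 is full ascertainment.

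**Hand check of missed deaths at q = 0**

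With λ = ln 2/median and follow-up running from a to b months:

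- number alive at cutoff = 170 × (e^(−λa) − e^(−λb)) / (38λ)
- missed deaths ≈ number alive × λ × w/2, where w/2 = 1.38 months

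For median 14.4, λ = 0.0481:

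- Cutoff at 3 months (a = 3, b = 41): 67.6 alive; 67.6 × 0.0481 × 1.38 = 4.5 missed.
- Cutoff at 9 months (a = 9, b = 47): 50.7 alive; 3.4 missed.

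For median 8.9, λ = 0.0779:

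- Cutoff at 3 months: 43.1 alive; 4.6 missed.
- Cutoff at 9 months: 27.0 alive; 2.9 missed.

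The simulation below gives slightly more, because those who die in the gap were also at risk at the last contact.

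**Simulation at q = 0 (2,000 replicates, mean Kaplan-Meier results)**

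| True median | Cutoff after accrual | Missed deaths | Median OS, full information | Median OS, SAP rule | Difference | 18-month rate |
|---|---|---|---|---|---|---|
| 8.9 | 3 months | 4.8 | 8.97 | 9.26 | +0.30 | 24.6% to 26.1% |
| 8.9 | 9 months | 3.1 | 8.95 | 8.99 | +0.04 | 24.6% to 25.5% |
| 14.4 | 3 months | 4.6 | 14.49 | 15.09 | +0.59 | 42.0% to 43.6% |
| 14.4 | 9 months | 3.5 | 14.48 | 14.75 | +0.27 | 42.0% to 42.8% |

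The 12-month rate rises by 0.5 to 1.4 points in the same four cases.

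**Dependence on ascertainment**

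At q = 0.5 the SAP rule's upward shift in the median is 0.02 to 0.29 months. At q = 1 it is zero in all four cases.

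**Last-known-alive censoring for everyone, with no status update**

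At q = 0 this agrees with full information to within 0.04 months. At q = 1, deaths count up to the cutoff while survivors are cut back to their last contact, so the median falls:

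- median 8.9: 8.96 to 8.71 (3 months) and 8.97 to 8.90 (9 months)
- median 14.4: 14.55 to 14.02 (3 months) and 14.49 to 14.25 (9 months)

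That is a downward shift of about 0.1 to 0.5 months. If a status update at cutoff finds every death and confirms every survivor, each subject has either a true death date or confirmed follow-up to the cutoff, and the full-information result is recovered.

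**The case against.** The strongest reply is that this is ordinary administrative censoring. The sentence already sends lost and withdrawn subjects, in whom unverified time would be longest, to the last date known alive. The rest can be read as subjects established alive at the cutoff, and censoring them there is unbiased.

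The worst case is also unlikely. The protocol assesses OS throughout the study. Subjects on treatment are seen on Days 1 and 8 of each 21-day cycle. Serious adverse events, including fatal ones, are collected for up to 90 days after the last dose and reported within 24 hours of awareness. Protocol 9.1.3 continued survival follow-up beyond the primary-analysis cutoff, so a later contact could settle status at the cutoff. Any check may also sit in programming specifications that are not in these documents.

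Most of this stands, and it limits the point to a conditional and small one. It does not remove it: the benign reading depends on a confirmation step that neither document requires, and SAP 6.2.2 points to status at a visit before the cutoff.

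A reader might infer three stronger things:

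- **That OS is biased upward.** The documents show only that it can be. The bias needs deaths that are unknown at analysis, and nothing in the documents says how complete ascertainment was.
- **That Amendment 05 makes the bias large.** It would grow if OS were analysed long after follow-up stopped. But the SAP is written to Amendment 04, the Amendment 05 rationale for ending central scan reading refers to a completed final efficacy analysis, and no later OS update is described.
- **That efficacy conclusions are affected.** The primary decisions rest on ORR. Table 1 lists historical OS medians, but no formal OS comparison with them is planned.

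**Conclusion.** The point holds in conditional form and is minor. The SAP allows unverified time to count as OS follow-up for subjects who are neither dead, lost nor withdrawn. If no death after the last 12-weekly contact is known at analysis, about 3 to 5 deaths in 170 are missed, median OS rises by less than 0.1 to 0.6 months, and the 18-month rate rises by 0.8 to 1.6 points. If status is confirmed at cutoff, the bias is zero.

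For scale, the binomial 95% half-width for a rate of 42% with 170 subjects is 1.96 × √(0.42 × 0.58/170) = 7.4 points, before any widening for censoring. These sizes rest on the assumed cutoff, exponential survival and 12-weekly contact for all subjects. More frequent contact on treatment would make them smaller. OS is descriptive and secondary, and no test or primary conclusion changes.

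**What to change.** Replace the OS rule in SAP section 8 with text to this effect:

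- Subjects confirmed alive on or after the data cutoff are censored at the cutoff.
- All other subjects not known to have died by the cutoff are censored at the last date known alive on or before it.
- A vital-status update is obtained for all subjects in survival follow-up at the OS cutoff, so that deaths and survivors are ascertained alike. The SAP states which cutoff applies to OS, given that Amendment 05 ended follow-up.

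The third item is needed. Moving everyone to the last date known alive without a status update can lower median OS by about 0.1 to 0.5 months when deaths are reported promptly but survivors' dates are not refreshed. The cost is two or three sentences in the SAP and a modest round of status checks at the cutoff.

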9.4.6.3 Prohibited Concomitant Therapies and Drugs

Subjects should not receive other antitumor therapies while on study. If subjects receive additional antitumor therapies, such as chemotherapy, hormone therapy, or immunotherapy, this will be judged to represent evidence of disease recurrence or progression, and study drug will be discontinued. These subjects should complete all off-treatment assessments and continue to be followed for survival in the Posttreatment Phase.

Subjects are prohibited from receiving the following therapies during the Screening and Treatment Phase of this study:

- Antineoplastic systemic chemotherapy or biological therapy
- Immunotherapy not specified in this protocol
- Chemotherapy not specified in this protocol
- Investigational agents other than eribulin mesylate and pembrolizumab
- Radiation therapy
 - Note: Radiation therapy to a symptomatic solitary lesion or to the brain may be considered on an exceptional case-by-case basis after consultation with sponsor. The subject must have clear measurable disease outside the radiated field. Administration of palliative radiation therapy will be considered clinical progression for the purposes of determining PFS.
- Live vaccines within 30 days prior to the first dose of study treatment and while participating in the study. Examples of live vaccines include, but are not limited to, the following: measles, mumps, rubella, varicella/zoster, yellow fever, rabies, BCG, and typhoid vaccine. Seasonal influenza vaccines for injection are generally killed

virus vaccines and are allowed. However, intranasal influenza vaccines (eg, FluMist[®]) are live attenuated vaccines, and are not allowed.

- Systemic glucocorticoids for any purpose other than to modulate symptoms from an AE that is suspected to have an immunologic etiology. The use of physiologic doses of corticosteroids may be approved after consultation with the sponsor.
 - Note: Inhaled steroids are allowed for management of asthma.

For subjects who, in the assessment by the investigator, require the use of any of the aforementioned treatments for clinical management, continuation of the study medication and further participation in the study must be discussed and agreed upon with the sponsor. Subjects may receive other medications that the investigator deems to be medically necessary

There are no prohibited therapies during the Post-Treatment Follow-up Phase.

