Censoring rule for PFS by RECIST 1.1

The PFS derivation rules in this SAP follow the sensitivity of analyses described in Food and Drug Administration (FDA) “[Guidance for Industry Clinical Trial Endpoints for the Approval of Cancer Drugs and Biologics \(2007\)](#)”.

Definition of Progression Date: Progression date is assigned to the first time at which radiological progression can be declared.

For progression based on a new lesion, the progression date is the date of the initial detection of the new lesion, if there were multiple new lesions detected, then the earliest date of initial detection will be used.

Table 3 shows the primary censoring rules for the derivation of PFS based upon investigator's tumor assessment.

Censoring rule for irPFS by irRECIST

Definition of progression date by irRECIST (i.e., irPD):

- For the subjects who experience PD by RECIST 1.1 and then confirmed by irPD ($>$ or <28 days) or not confirmed due to any reasons, the first documented PD date by RECIST 1.1 is the date of irPD.
- For the subjects who experience PD by RECIST1.1 and then followed by irCR/irPR/irSD, the first documented progression date is the date of first irPD defined by irRECIST.
- If the subject had new lesion earlier than overall timepoint response of PD in irRECIST, the date of new lesion is not counted as irPD date. (this is different from PD by RECIST 1.1 for which, as soon as subject developed new lesions, subject is considered as PD and PD date is the date of new lesion).

Censoring rule will be same as RECIST1.1 except that for the second rule in [Table 3](#).

“Date of first radiologic PD assessment” means the irPD Date determined as above.

Duration of Response

Duration of Response (DOR) – defined as the time from the date that a confirmed objective response is first documented to the date of PD or death due to any cause for those subjects with a confirmed PR or CR. For subjects who did not experience PD or death by the end of data cut off, the date of last adequate radiologic assessment before missing tumor assessments or new anti-cancer therapy will be used as censoring date.

BOR, PFS and DOR will be defined separately for IIR data and for investigator reviewed data following the same rules.

Table 3. Censoring Rules for Analysis of Progression-Free Survival

No.	Situation	Date of Progression or Censoring	Outcome
1	No baseline or post-baseline tumor assessments	Date of the first dose	Censored

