2	Progression documented between scheduled visits	Date of first radiologic PD assessment	Progressed
3	No progression at the time of data cut-off	Date of last adequate radiologic assessment prior to or on date of data cut-off	Censored
4	New anticancer treatment started	Date of last adequate radiologic assessment prior to or on date of new anticancer treatment	Censored
5	Death before first PD assessment	Date of death	Progressed
6	Death between adequate assessment visits*	Date of death	Progressed
7	Death or progression after two or more missed visit**	Date of last adequate radiologic assessment before missed tumor assessments	Censored

CR = complete response, PD = progressive disease, PR = partial response, SD = stable disease,

* Adequate tumor assessment is a radiologic assessment of CR, PR, SD, non-CR/non-PD or PD as determined by investigators.

New anticancer treatment includes palliative radiotherapy. Any tumor assessments after new anticancer treatment started will be removed in the definition of PFS.

** More than two missed visits is defined if the duration between the last tumor assessment (including NE) and death or PD is longer than 126 days (18 weeks) or 168 days (e.g. 24 weeks) for subjects on the every 9 or 12 week scanning schedule in this study:

The priority of the censoring rules is as follows:

1. If the subject had PD or death, the following sequence will be applied:

- If a subject did not have baseline tumor assessment (No. 1), the subject will be censored on date of the first dose. However, if the subject did not have baseline tumor assessment and died within 126 days (18 weeks) after the first dose and did not receive new anticancer treatment, the date of death will be the PFS event date (not censored).
- If a subject had new anticancer treatment before PD or death (No. 4), the subject will be censored on the date of the last adequate tumor assessment prior to or on the date of new anticancer treatment.
- If a subject missed two assessments before PD or death (No. 7), the subject will be censored on the date of the last adequate tumor assessment before PD or death. Note that if a subject is censored by both this criterion and the anticancer treatment criteria, the earliest

censoring date will be used.

- Otherwise, if a subject had an event (No. 2, No. 5, or No. 6), the earliest event date will be used.

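### Read literally, the SAP counts a responder's death after new anticancer therapy or missed scans as a DOR event, while its PFS rules censor the same subject

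*SAP*

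**What the plan says.** **DOR.** SAP Section 8 (Duration of Response) runs DOR from the first documentation of a confirmed response "to the date of PD or death due to any cause for those subjects with a confirmed PR or CR". One censoring sentence follows. It opens "For subjects who did not experience PD or death by the end of data cut off, the date of last adequate radiologic assessment" and ends "before missing tumor assessments or new anti-cancer therapy will be used as censoring date". New therapy and missed assessments appear only inside that sentence.

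**PFS.** Table 3 and the priority list beneath it have separate branches for subjects who had PD or death and for subjects who did not. In the first branch: "If a subject had new anticancer treatment before PD or death (No. 4), the subject will be censored" at the last adequate assessment on or before that treatment (No. 4). Two missed assessments before PD or death also lead to censoring (No. 7). A Table 3 footnote adds: "Any tumor assessments after new anticancer treatment started will be removed in the definition of PFS". The best-overall-response rules delete such scans too. The DOR paragraph has no such statement.

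**Which rule governs DOR.** Protocol 9.7.1.6.2 leaves DOR censoring to the SAP. SAP 6.4.2 says Section 8 gives the rules variable by variable, and Table 3 is titled for PFS only. One line sits between the two: "BOR, PFS and DOR will be defined separately for IIR data and for investigator reviewed data following the same rules".

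**The concern.** A responder who moves to another therapy without documented progression and then dies did experience death by cutoff. The DOR censoring sentence therefore does not reach that subject, and the death date ends the response. If the same subject is alive at cutoff, the sentence does apply and DOR is cut back to the last adequate scan before the new therapy. So whether time on the next therapy enters DOR depends on whether the subject died. PFS has no such dependence, because No. 4 censors either way.

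The situation can arise. Protocol 9.4.6.3 says "There are no prohibited therapies during the Post-Treatment Follow-up Phase". Imaging after discontinuation stops when new anticancer treatment starts (Protocol 9.5.1.4.1), while survival follow-up continues (Protocol 9.3.3). Amendment 05 later ended follow-up assessments, but the SAP is written to Amendment 04. After a switch, the later event on record will therefore usually be a death.

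At stake is the reading of DOR beside ORR. Some responders would be events in one time-to-event endpoint and censored in the other, with no stated reason.

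**Working it through.** No figure in the plan depends on this rule, so there is nothing to reproduce. The check applies both rules to the same subject and then sizes the effect under assumed inputs.

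**1. One subject (assumed dates, in weeks from first dose).** Response at 9, last adequate scan without PD at 27, new therapy at 30, death at 40.

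| Rule | Outcome | Time |
|---|---|---|
| DOR as written | Event at death | 40 − 9 = 31 weeks |
| PFS, Table 3 No. 4 | Censored at last adequate scan | 27 weeks |
| DOR if No. 4 applied | Censored at last adequate scan | 27 − 9 = 18 weeks |

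The gap from scan to death is 40 − 27 = 13 weeks, below the 18-week limit for No. 7. It is therefore the new-therapy rule that separates the endpoints here.

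**2. Missed assessments.** Take the same subject with no new therapy and no scan after week 27. On the 9-week schedule, a death later than week 27 + 18 = 45 is censored for PFS under No. 7. For DOR it is still an event at death.

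**3. Subjects affected.** The plan does not give the share of responders who switch before PD; 10% to 30% is assumed.
- At ORR 25% (the Stratum 2 alternative) of 165 evaluable: 0.25 × 165 ≈ 41 responders, so about 4 to 12 affected.
- At ORR 35% (the all-subject expectation): 0.35 × 165 ≈ 58 responders, so about 6 to 17 affected.

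**4. Event count.** Let f be the share switching before PD. With complete follow-up every subject has an event under the written rule, and only 1 − f do under PFS-style censoring. The relative increase is f/(1 − f):
- f = 10%: 0.10/0.90 = 11%
- f = 30%: 0.30/0.70 = 43%

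This needs every switcher to have died by cutoff. With cutoff assumed uniform from 6 to 24 months after response, median DOR 6 to 10 months and median post-switch survival 6 or 9 months, simulation gives about 5% to 28%.

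A second simulation assumed a median of 36 weeks to PD, 7% to 26% switching before PD, median post-switch survival of 13, 26 or 52 weeks, and cutoff 52 to 130 weeks after response. The share of responders with an event was 78% to 87% as written and 62% to 77% with PFS-style censoring. Scenario by scenario, the increase runs from 0.802/0.763 − 1 = 5% to 0.872/0.624 − 1 = 40%. The 40% case has 26.1% switching, where f/(1 − f) = 0.261/0.739 = 35%. The complete-follow-up figure is thus the upper part of the range and not a strict ceiling: deaths soon after a switch can precede cutoff more often than progression does.

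**5. Median.** With complete follow-up and the step 4 medians, the written rule moves median DOR by −0.7 to +0.3 months and the 12-month rate by about −3 to +3 points. In the second simulation the median was 30.7 to 35.5 weeks as written against 33.6 to 35.7 with PFS-style censoring, a shift of about −3.1 to +0.8 weeks. The sign depends on how soon death follows the switch. For scale, with 41 responders and a true median of 8 months, an order-statistic 95% interval for the median spans roughly 5 to 13 months.

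**The case against.** **The intent may already be to match PFS.** The DOR sentence names the same triggers as Table 3 Nos. 3, 4 and 7. The same-rules line and Table 3 follow directly. The second item of the priority list covers subjects without PD or death, yet it lists No. 7, which is defined by death or progression after missed visits. The authors may therefore use that phrase loosely, to mean no countable event. This stands as a reason to call the intent unclear. It does not remove the problem: the same-rules line most naturally concerns independent versus investigator data, and a programmer following the DOR sentence would code the literal rule.

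**PFS is not a clean benchmark.** Protocol 9.4.6.3 treats additional antitumor therapy as evidence of recurrence or progression, and palliative radiation as clinical progression for PFS. SAP Section 8 censors at both. Table 3 also defines an adequate assessment by the investigator's reading, which does not suit the independent-review analysis. Both points stand, so Table 3 should not be copied unedited.

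**Counting deaths is a legitimate choice, and censoring at new therapy may be informative**, for example when the investigator switched because of suspected progression. This stands and is why a sensitivity analysis is needed.

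**The independent-review case is narrower than it looks.** A reader might infer that a responder stopped for investigator-called PD that independent review did not call has no later scan. Protocol 9.5.1.4.2 has clinically stable subjects re-imaged at 4 weeks or more, and scans went to the core laboratory until Amendment 05. A later scan would often exist; the case fits mainly clinically unstable subjects.

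**Conclusion.** The inconsistency is real on the literal text: the same responder can be a DOR event at death and censored for PFS, and the SAP does not explain why. DOR is a secondary endpoint described by Kaplan–Meier estimates, so neither ORR test is affected.

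The event count is the quantity that changes. Its size rests on assumed switching, post-switch survival and follow-up: 11% to 43% with complete follow-up, less in most scenarios with a realistic cutoff. The median shift is likely small relative to its sampling error.

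Three stronger readings are tempting and not supported:
- **That DOR is inflated in favour of the combination.** A response at month 2, switch at month 6 and death at month 20 would give an 18-month DOR event. But that subject survives 14 months after switching; with median post-switch survival of 6 or 9 months, only 0.5^(14/6) = 20% to 0.5^(14/9) = 34% do so. The simulated median moves in either direction.
- **That the DOR intervals are falsely narrow.** More events usually mean narrower intervals, but no interval was computed under the two rules, and deaths after a switch are real events under a different estimand.
- **That the sponsor deliberately chose opposite rules.** The text supports only an unexplained difference with unclear intent.

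**What to change.** In SAP Section 8, replace the DOR censoring sentence with a statement that:

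- DOR uses the Table 3 event, censoring and priority rules (Nos. 2 to 7), counted from the first documented confirmed response;
- this applies to DOR by independent review, by investigator and by irRECIST;
- an adequate assessment is judged by the reviewer whose data are being analysed.

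Report DOR with all deaths counted as events (the current literal rule) as a sensitivity analysis, because censoring at new therapy may be informative. At the same time, reconcile the handling of new anticancer therapy and palliative radiation in SAP Section 8 with Protocol 9.4.6.3, so that PFS and DOR do not both carry that conflict.

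Cost: a short SAP edit, a small programming change and one extra table. The downside is somewhat fewer DOR events, wider intervals and possibly informative censoring in the main DOR analysis.
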